I. Objectives

Our previous research has shown that children exposed to media characters with guns in movies¹ and video games² are more likely to use real guns themselves (e.g., touch them, hold them, pull the trigger). This research tests whether exposure to a gun safety video a week before the study can help counteract dangerous behavior around guns.

II. Background and Rationale

Guns are prominent in movies that target children. An analysis of top selling films found that the depiction of guns in violent scenes in PG-13 films that target youth has increased from the level of G and PG files in 1985 when the rating was introduced, to the level of R films by 2005, to exceed the level of R films since 2012,³ a trend that has continued.⁴ By definition, a PG-13 movie is supposed to have less violence than an R-rated movie. The Motion Picture Association of America says on its website that the violence in a PG-13 movie “does not reach the restricted R category.” Our study shows that it does.

Previous research has shown that when exposed to movie characters that smoke, children are more likely to start smoking themselves⁵; the same is true for characters that drink alcohol⁶. Similarly, research in our lab has shown that children are more to use guns (e.g., handle them, pull the trigger) after exposure to movie characters who use guns.¹ We replicated this study using video games,² and also found that children who had taken a gun safety course were less likely to engage in dangerous behavior around firearms. However, it is difficult to draw causal inferences about the gun safety course because children were not randomly assigned to take or not take a gun safety course.

The present research will aim to reduce dangerous behavior around firearms by first exposing participants to a gun safety video recorded by The Ohio State University Chief of Police. The control video is about car safety. Children will see the videos about a week before they come into the lab. We predict that children will be less likely to engage in dangerous behavior around real firearms if they saw the gun safety video than if they saw the car safety video, even if they see a movie with guns in the lab.

III. Procedures

A. Research Designs, Samples, Measures, and Procedures

Design

The experiment will test the effects of the mere presence of guns in movies on dangerous behavior with guns in children. Participants will be children 8-12 years old. Children will be tested in pairs. Each child will bring a sibling, relative, or friend to the study. Participants and partners will each receive a \$30 gift card (\$5 for watching the safety video at home and \$25 for doing the lab study). The behavioral measure will be whether or not children handle a real (but non-firing) gun and whether they pull the trigger, including at themselves or their partners.

The design will be a 2 (movie clip-guns present vs. movie clip-guns absent) x 2 (gun safety video vs. seatbelt safety video) between-subjects design. Participants will be randomly assigned to conditions, but both children in the dyad will watch the same safety video.

We predict a main effect for type of movie (i.e., children who see movie characters use guns will be more likely to use real guns themselves than will children who do not see movie characters use guns), a main effect for type of safety video (i.e., children who see the gun safety video will be less likely to use real guns themselves than will children who see the car safety video), and an interaction between type of movie and type of safety video (i.e., the movie with guns will have a weaker effect on children who see a gun safety video than on children who see a car safety video).

Procedure

Participants will be told that the study is about what children like to do for fun, such as watch videos and play with toys and games. Participants who agree to participate in the study will be sent consent (adult) and assent (child) forms electronically, along with a pretest for both adult and child to complete, should they consent and assent to participating in the study. These pretests were used in our previous research.^{1,2} After informed consent is obtained, the participants will be sent the safety video for the condition to which they are assigned (i.e., gun vs. car safety video), a short questionnaire about the video, and a \$5 electronic gift card. Approximately one week after being sent the video, the participants will come to the lab for the study.

Experimenters and research assistants will be wearing masks at all times and will be fully vaccinated against COVID-19. The lab space will be sanitized between sessions to ensure participant safety.

Per OSU policy, all visitors to Ohio State campuses and medical facilities are required to wear masks indoors, regardless of their vaccination status. Children participating in the study and their observing parent or guardian will be required to wear masks for the duration of the experiment in the lab. Outdoor mask wearing is also required on campus for individuals who are unvaccinated when they are unable to maintain socially distancing.

As in our previous study¹, we are using two PG-rated (i.e., "Parental Guidance Suggested. Some Material May Not Be Suitable For Children") Disney films (*National Treasure*, *Rocketeer*) that have been edited to be about 20 minutes. There will be two versions of each film clip, one version with guns left in and one version with guns edited out. Thus, there are four film clips: (1) *National Treasure* with guns, (2) *Rocketeer* with guns, (3) *National Treasure* without guns, and (4) *Rocketeer* without guns.

Participants will be tested in pairs. After viewing the film clip, participants will be placed in a room containing games and toys, with hidden cameras. Participants will be told that

they can play with any of the games and toys in the room for the next 20 minutes. Some games and toys will be scattered about the room, and some will be placed in drawers. Included in the toys are Nerf guns and swords. Two real handguns will be placed in a separate drawer, as in our previous research.^{1, 2} The handguns have been modified so they cannot fire. Inside the magazine, the handgun contains no bullets. Instead, it contains a sensor that counts the number of times the trigger is pulled with sufficient force to discharge the gun. This allows us to distinguish reliably the children who pull the trigger from those who handle the gun but do not pull the trigger. Parents will be asked to predict whether their child will tell an adult if they find the guns, and whether they will handle a gun and pull the trigger. The researcher and the parents will be able to watch the session via a monitor in a control room.

After the 20-minute play period, children will complete a posttest that consists of an attitudes toward guns measure, as in our previous research.^{1, 2}

A thorough debriefing will follow.

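### The protocol fixes only the safety video within a dyad, so partners may see different movie versions; if they do, imitation between them would be expected to dilute the movie effect

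*Protocol*

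**What the plan says.** Protocol section III.A, Design, sets out a factorial trial: "The design will be a 2 (movie clip-guns present vs. movie clip-guns absent) x 2 (gun safety video vs. seatbelt safety video) between-subjects design". The allocation rule follows: "Participants will be randomly assigned to conditions, but both children in the dyad will watch the same safety video". The unit named is the participant, and the safety video is the only factor tied to the pair. No such rule is given for the movie in either document.

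The same section predicts a movie main effect, a safety-video main effect and an interaction in which "the movie with guns will have a weaker effect on children who see a gun safety video" than on children who see the car video. Its behavioural measure covers handling the gun and "whether they pull the trigger, including at themselves or their partners".

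Protocol section III.A, Procedure, says "Participants will be tested in pairs" and then "After viewing the film clip, participants will be placed in a room containing games and toys, with hidden cameras". Play lasts 20 minutes. On the guns it says "Two real handguns will be placed in a separate drawer, as in our previous research".

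Protocol section III.C rates threats to internal validity as low because the study is a laboratory experiment; it does not discuss influence between partners. The SAP's Data Analyses section lists models with experimental conditions plus gender, or plus covariates. It names no dyad term and no term for the partner's movie.

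**The concern.** If the movie version is allocated child by child, a child who saw the clip without guns may spend the play period beside a partner who saw guns used. What the partner does with a real gun is then part of that child's exposure. The protocol's own rationale is that children use guns more after watching others use them, so imitation between partners is a reasonable expectation. The outcomes are also entangled directly: a trigger pull can be aimed at the partner, and one child's discovery of the drawer opens it to both.

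Two of the three stated predictions, the movie main effect and the interaction, depend on the movie contrast. The question is what that contrast estimates when partners may have seen different versions. This is separate from the standard errors: a dyad intercept would account for correlation within pairs but would not turn the contrast into a same-movie effect.

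**Working it through.** **Inputs from the documents.** Section III.B takes an earlier sample of 104 and doubles it: 2 × 104 = 208 children, which reproduces. Tested in pairs, that is 208/2 = 104 dyads. The documents give no effect size, IRR, within-dyad correlation, spillover size or power calculation. Every such value below is an assumption.

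**How many dyads would be mixed.** With independent allocation by child, half of dyads are expected to be discordant: 104 × 1/2 = 52. With a fixed 104:104 split of children the figure is 104 × 104/207 = 52.25, so again about 52.

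**Model.** For each child, log rate = μ + β × (own movie) + δ × (partner's movie) + dyad effect. Let s = δ/(β+δ) be the share of the log effect that comes through the partner.

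- Both partners on the same version: IRR = exp(β+δ).
- Independent allocation by child: the partner's movie is unrelated to the child's own, so the own-movie contrast is exp(β) = (same-movie IRR)^(1−s).

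**Movie effect (assumed same-movie IRR 2.0) and interaction (assumed IRR 3.0 with the car video, 1.5 with the gun video, ratio 0.50; same s in both arms).**

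| s | Movie IRR, allocation by child | Interaction ratio, allocation by child |
|---|---|---|
| −0.25 | 2^1.25 = 2.38 | 0.5^1.25 = 0.42 |
| 0 | 2.00 | 0.50 |
| 0.25 | 2^0.75 = 1.68 | 0.5^0.75 = 0.59 |
| 0.50 | 2^0.50 = 1.41 | 0.5^0.50 = 0.71 |

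A simulation with over-dispersed counts and a dyad effect agreed closely (car-video arm, s = 0.50: 1.76, against 3^0.5 = 1.73 in closed form).

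**Unequal spillover by video arm.** With s = 0 under the car video and 0.5 under the gun video, the ratio is 1.5^0.5/3 = 0.41. With the shares reversed it is 1.5/3^0.5 = 0.87. The true ratio is 0.50 in both cases, so the interaction can move either way.

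**Cost of a common movie.** For pairs the design effect is 1+ICC, so effective N = 208/(1+ICC): 189, 160 and 139 at ICC 0.1, 0.3 and 0.5. As a rough guide, take an assumed standardised difference d = 0.5 at two-sided 0.05 and a normal approximation.

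- Same movie within pairs: power = Φ(d/√(2(1+ICC)/104) − 1.96) = 0.93, 0.89 and 0.84 at those three ICCs.
- Allocation by child: power = Φ(d(1−s)/√(2/104) − 1.96) = 0.95, 0.77 and 0.44 at s = 0, 0.25 and 0.50. The ICC roughly cancels here because own and partner allocation are independent.

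A shared movie therefore costs a little power if there is no spillover. In this illustration it keeps more power than allocation by child when s is 0.50, and at s = 0.25 too.

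**The case against.** A reader might infer that the protocol plans to mix movies within pairs. It does not say that. The Procedure section puts "Participants will be tested in pairs" close to a reference to one film clip, which reads naturally as a pair watching together. The safety video is sent to participants about a week before the visit, so there was a particular reason to state that it is common, while the movie belongs to a session already run in pairs. This stands: the text is ambiguous. It does not settle the matter, because the singular can be generic. The same section uses the singular for the safety video sent to participants in different conditions.

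A reader might also infer that mixed pairs must bias the movie effect and the interaction toward the null. The documents do not support that. With no spillover there is no dilution. With negative spillover, for example if a child primed by the movie monopolises the guns, the shift is away from the null. If spillover differs between video arms, which is plausible for a video meant to change behaviour around guns, the interaction can move in either direction.

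Dilution is also relative to a target. The predictions compare children who do and do not see guns in the movie, which can be read as the effect of the child's own exposure. In the model above, independent allocation returns that effect, β, without attenuation. The shortfall is against the same-movie effect.

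Finally, it would be wrong to call the same-movie effect unrecoverable under allocation by child. The partner's version would be randomised too, so a partner-movie term identifies both components, and about 52 dyads would be concordant. What stands against the plan is that the SAP specifies no such term.

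**Conclusion.** The point holds as an unresolved allocation rule with a conditional consequence. As written, the movie version is not tied to the dyad, and nothing in the analysis plan handles partners who saw different versions. If versions are mixed, imitation would be expected to dilute the movie effect relative to the same-movie effect: on an assumed IRR of 2.0, to 1.68 or 1.41 at spillover shares of 0.25 or 0.50.

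This rests on positive spillover, on the same-movie effect as the target and, for the interaction, on similar spillover in both video arms. No document gives a figure for any of these. The matter should be corrected because two of the three predictions depend on it and the change is small. If pairs did always share a clip, the correction merely records what was done.

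**What to change.** Replace the allocation sentence in Protocol section III.A, Design, with wording to this effect: *Each dyad is randomised as a unit to one of the four movie-by-safety-video cells, so that partners receive the same safety video and the same movie version.* In the SAP's Data Analyses section, account for dyad clustering with a dyad random effect or cluster-robust standard errors. The safety video is a dyad-level factor in any case, so this is needed whichever rule applies to the movie.

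If any dyads were run with mixed versions, flag them, add the partner's movie version to the model (and its product with safety video for the interaction), and report the movie and interaction effects with and without those dyads.

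The cost is one sentence, a dyad-level allocation list and a line in the SAP. The statistical price is that the movie comparison becomes wholly between dyads, with an effective sample size of about 160 rather than 208 at an assumed ICC of 0.3.

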Preliminary bivariate and chi-squared tests will be run on the outcome variables. As in our prior studies^{1,2}, two sets of models will be run: (1) a reduced model that includes experimental conditions and gender, and (2) a full model that includes experimental conditions and covariates.

Incidence rate ratios (IRRs) with *SEs*, *z*-tests, and the corresponding 2-tailed *p*-values will be reported for both types of models. Nonsignificant variables (at the 2-tailed .05 significance level) will be excluded from models.

¹ <https://jamanetwork.com/journals/jamanetworkopen/fullarticle/2734799>

² <https://jamanetwork.com/journals/jamapediatrics/fullarticle/2654597>

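### Two film titles are crossed with gun content, but film title is neither a prespecified model term nor given an allocation rule; the likely cost is small and the remedy is cheap.

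*Protocol*

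**What the plan says.** Protocol III.A, Procedure, names two PG-rated films and explains that "There will be two versions of each film clip, one version with guns left in and one version with guns edited out". It concludes "Thus, there are four film clips". Title is therefore fully crossed with gun content.

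Protocol III.A, Design, describes a "2 (movie clip-guns present vs. movie clip-guns absent) x 2 (gun safety video vs. seatbelt safety video) between-subjects design". Title is not one of the factors. On allocation it says only this: "Participants will be randomly assigned to conditions, but both children in the dyad will watch the same safety video". No sentence says how a title is chosen, whether titles are balanced over the four cells, or whether the two children in a pair see the same clip.

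SAP, Data Analyses, specifies "a reduced model that includes experimental conditions and gender" and a full model with the conditions plus covariates. It does not define the conditions or list the covariates. The same section removes from the models any variable that is not significant at the two-sided 0.05 level. SAP, Data Collection, lists the variables to be recorded. Film title is not among them; the nearest entry is the child's evaluation of the movie.

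**The concern.** The investigators set the film title before any outcome is seen, so it is a natural term for the model. Two things are at stake if it is left out.

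- **Precision.** If one film provokes more gun handling than the other, the difference goes into the estimated dispersion and widens the standard errors.
- **Balance.** If the two titles are unevenly spread over the groups being compared, part of the film difference is carried into the estimated effect of gun content or safety video.

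There is also a question of discipline. A term that is not named in advance can be added or left out after the data are seen. If it were entered as an ordinary covariate, the dropping rule could remove it.

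**Working it through.** **Plan's own figure.** Protocol III.B doubles a previous sample of 104: 2 x 104 = 208, which reproduces. It does not depend on film title. The documents give no power, effect size, mean count, dispersion or film effect, so everything below except the sample size is an assumption, shown as a range.

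**Inputs.** 208 children, hence 104 per level of each factor, or 104 pairs and 52 pairs per level. Negative binomial variance is mu + a·mu², with a the dispersion. Film rate ratio r is 1, 1.5, 2 or 3. Children are treated as independent, although they are tested in pairs.

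**Step 1: precision by formula, titles balanced.** Leaving out a 50/50 film factor raises the dispersion from a to a + c²(1 + a), where c = (r − 1)/(r + 1).

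Take a = 3, mean 3, r = 2:
- c² = (1/3)² = 0.111, so the dispersion becomes 3 + 0.111 x 4 = 3.444.
- Without film: variance = (2/104)(1/3 + 3.444) = 0.0726, SE 0.270.
- With film (film means 2 and 4): information per level = 52 x (2/7 + 4/13) = 30.86, variance = 2/30.86 = 0.0648, SE 0.255.
- Fall in variance: 1 − 0.0648/0.0726 = 11%.

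Over a = 1 to 6 and means of 1 to 10, the SE without film is larger by 1.5–3.4% (r = 1.5), 4–9% (r = 2) and 8–19% (r = 3), and by 0% at r = 1.

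**Step 2: precision by refitting.** The formula uses the variance of a simple ratio of means when film is omitted. A fitted negative binomial model re-estimates its own dispersion, so the formula overstates the gain in model variance. Simulated trials (208 independent children, titles balanced within cells, mean 3, dispersion 1 to 5) were fitted with and without film. The fall in model variance of the safety-video log IRR was:

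| Film ratio | Fall in model variance |
|---|---|
| 1 | none |
| 1.5 | about 0–3% |
| 2 | about 2–7% |
| 3 | about 5–16% |

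The larger falls belong to dispersion 1 and the smaller ones to dispersion 5.

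**Step 3: bias and power, titles balanced.** With a true safety-video IRR of 0.5, the mean estimate was about 0.50 with or without film. At dispersion 3 (400 runs per setting), power without and with film was 0.787 and 0.795 (r = 1.5), 0.715 and 0.755 (r = 2), and 0.735 and 0.785 (r = 3). At r = 1 it was 0.770 and 0.762, so differences of about 0.01 are noise.

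**Step 4: titles unbalanced.** If the second film has share q1 in one group and q0 in the other, the unadjusted IRR is multiplied by (1 − q1 + q1·r)/(1 − q0 + q0·r).

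| Film ratio | 55/45 vs 45/55 | 60/40 vs 40/60 |
|---|---|---|
| 1.5 | 1.275/1.225 = 1.04 | 1.3/1.2 = 1.08 |
| 2 | 1.55/1.45 = 1.07 | 1.6/1.4 = 1.14 |
| 3 | 2.1/1.9 = 1.11 | 2.2/1.8 = 1.22 |

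If each of 52 pairs per level were given a title by simple randomisation (two independent binomials, n = 52, p = 0.5), the shares would differ by at least 10 points about 28% of the time and by at least 20 points about 4% of the time.

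**Step 5: films that differ only when guns are shown.** A film main effect is then misspecified. In the same kind of simulation its gain in model variance was close to nothing at r = 1.5 and only about 5–7% at most at r = 3.

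**The case against.** **The full model may include film.** Its covariates are never listed and the SAP does not define the experimental conditions, so a reader might infer more than is written by saying that film is excluded from both models. That objection stands: the documents show only that film is not prespecified. It does not rescue the plan. The reduced model adds nothing but gender to the conditions, the Protocol defines the conditions without title, and a film covariate would still face the dropping rule. The movie evaluation is a rating given after exposure, not the title.

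**Averaging over two films is legitimate.** It is. Varying the stimulus broadens the result, and the loss is nil if the films do not differ. A reader might also infer that film is confounded with gun content or adds bias to every estimate. The documents do not support this: each title appears in both gun conditions, so with balance the IRR is unbiased and the main consequence is a somewhat conservative standard error.

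**One film term does not cure everything.** This also stands. If the films differ only in their guns-present versions, the main effect helps little, which is why the interaction should be reported as well.

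**The sizes are hypothetical and ignore pairing.** Correct. They are ranges under assumptions, not estimates for this trial.

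**Conclusion.** The point holds as a low-cost improvement, not as a flaw that threatens the trial. Film title is crossed with gun content, sits outside the 2 x 2, is absent from the reduced model, is unnamed in the full model and has no allocation rule.

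The practical gap is the missing allocation rule combined with the missing model term. With balance, the gain from a film term is probably small: single-figure percentages of variance for film ratios up to 2. Without balance, the estimate itself moves, by 8% to 22% at a 60/40 against 40/60 split for film ratios of 1.5 to 3. A split that uneven would be uncommon under simple randomisation by pair, but a milder one would not. These sizes rest on an assumed mean and dispersion, on independent children, and on film ratios that nothing in the documents supports or excludes.

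**What to change.** 1. In the SAP, name film title (*National Treasure* or *Rocketeer*) as a fixed two-level factor in both the reduced and the full model, and add it to the list of recorded variables.
2. Exempt it from the rule that drops nonsignificant variables.
3. In the Protocol, state that titles are balanced within each of the four cells, by pair if pairs share a clip. If allocation is already complete, report the number of children and pairs per title in each cell.
4. Report film by gun content as a sensitivity analysis, because a gun effect that differs by film is otherwise averaged and not seen.

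The cost is one degree of freedom in each main model and one more in the sensitivity analysis. No extra children or measurements are needed, only a record of which clip each child saw. Items 1, 2 and 4 are SAP edits and can be made even if allocation has finished.
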